2.0 Background and Significance

2.1 Background

The surgical invasiveness of elective total knee/hip arthroplasty (TKA/THA) in veterans provides a logical model under controlled conditions for evaluating physical therapy / occupational therapy (PT/OT) effectiveness after major lower extremity polytrauma sustained in the battlefield. The central idea of this protocol (in the grant application submitted to the Department of Defense) is to measure pain (primary) and rehabilitation (exploratory) outcomes after TKA/THA as influenced by factors under the direction of the anesthesiologist physician, specifically nerve block drug selection (plain bupivacaine versus the described 4-drug mixture as single-injection nerve blocks).

For these TKA/THA cases, our standard of care regional anesthesia (RegA) technique entails spinal anesthesia to ensure adequate anesthesia and excellent surgical conditions during surgery. Spinal anesthesia alone does not provide any sustained pain relief after surgery. As a result, our institutional standard of care for TKA/THA also entails single-injection nerve blocks (with the described 4-drug combination) of both L2-L4 and L4-S3 nerves/plexi, placed before surgery. Applying these nerve blocks before surgery ensures that our patients do not have significant pain after the spinal anesthetic “wears off” later in the day after surgery.

Nerve blocks can be administered as single-injections or via percutaneous indwelling catheters, the latter of which being far more labor-intensive and expensive.(1) We do not use indwelling perineural catheters at our institution. In the absence of the described 4-drug **MultiModal PeriNeural Analgesia** (MMPNA), the plain bupivacaine single-injection (0.1% - 0.25%) nerve block is typically reported as having 8-16 hr analgesic duration. In our institutional standard of care experience, the addition of clonidine-buprenorphine-dexamethasone (CBD) to bupivacaine 0.1% – 0.25% yields an average duration of analgesia of approximately 36 hr. We are unable to determine if this additional analgesic duration inhibits physical therapy after surgery (one of our exploratory aims for this specific study).

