4.0 Research Design and Methods

4.1 Type of Study

This is a single-site study that will take place at VA Pittsburgh Healthcare System, Pittsburgh, PA. It is a prospective randomized clinical trial evaluating the two different nerve block injection drugs for TKA and THA, introduced above and described further below. All described RegA techniques strategically avoid GETA and high-dose opioids, and the immediate postoperative complications (from GETA and high-dose opioids) that inhibit full-capacity cognitive function needed to accomplish PT/OT goals during the first 2 days after TKA/THA. Two hundred (200) total patients will be recruited and evaluated for study outcomes pre-TKA/THA (100 for TKA, 100 for THA). Following pre-surgical evaluation, patients will be block-randomized (stratified by [a] TKA vs. THA surgical procedure, [b] age, and [c] presence of diabetes). After surgery, all patients will undergo the same standardized PT/OT best-evidence care plans consistent with current clinical care at our institution. Evaluation of study outcomes will take place during the first two days after surgery, throughout the remainder of the hospital stay (which typically ranges from 2 to 5 days, including discharge day), and during the first two orthopedic post-op follow-up evaluations. The primary outcome is pain at 24 hr after surgery, and exploratory outcomes include physical therapy progress and anesthesia-related symptoms. We will also assess additional metrics of anesthesia and physical therapy success such as range of motion, physical function and performance testing, length of hospital stay, discharge placement, readmission, falls, and other adverse events.

Study Treatment Groups:

Institutional Standard of Care (ISOC)

All patients will receive a standardized bupivacaine spinal anesthetic, consistent with current institutional practice. All patients will receive pre-medications for the prevention of pain, nausea, vomiting, and gastroesophageal reflux, consistent with current institutional practice. All patients will receive intravenous hydration, intravenous antiemetics, and intravenous blood pressure support (e.g., intravenous phenylephrine bolus/infusion) consistent with our current institutional practice. The need for intraoperative blood transfusion will occur based on current institutional practice and collaborative decision-making between the surgical and anesthesia teams, consistent with current institutional practice.

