The tester uses a stopwatch to measure the amount of time the participant is able to stand on one limb. Time commences when the participant raises the foot off the floor. Time ends when the participant either: (1) uses the raised foot (moved it toward or away from the standing limb or touched the floor), (2) moves the weight-bearing foot to maintain his balance (ie, rotated foot on the ground), (3) a maximum of 45 seconds elapses. Three trials are performed in each side and recorded. This exam takes around 6 minutes.

Crude Sensory Examination: Sensory examination is carried out by touching lightly the patient in the specified anatomic distribution of L2-L4 and L4-S3 bilaterally, while the patient has his eyes closed. The patient is asked if the sensation is of equal intensity on both sides (normal), or if one side feels less than the other, or is unable to be felt (diminished or absent). This exam takes around 2 minutes.

Hip, Knee and Ankle Range of Motion: Range of joint movement is measured with a standard goniometer during passive (movement assisted by the tester) and active (without assistance by the tester) movements. Range of motion is tested with the subject lying in supine on the hospital bed or examination table. This is performed on both sides and recorded in degrees. Range of motion takes approximately 5 minutes.

Straight Leg Raise: The subject is asked to raise one lower extremity from the hospital bed up to approximately 45 degrees from the horizontal without bending the knee. The test is performed in both sides, and is recorded as “Yes” if the subject is able to raise the lower extremity higher than 20 degrees from the horizontal, or “No” if unable to lift the leg at that level. During this test the examiner also observes the presence of a knee extension lag, which is defined as a knee flexion (lag) equal or greater than 5 degrees during the straight leg raise. It takes approximately 3 minutes for the straight leg raise activity.

Stair climbing time: This test measures the time the subject takes to go up a flight of stairs. Subjects are instructed to use the handrail for safety purposes. The tester uses a stop watch to record time. It takes approximately 5 minutes for this test.

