Prolonged numbness in the distribution of the nerve blocks If a patient encounters numbness and weakness for an extended period of time after a nerve block is given, then certainly serious consideration is given to the possibility of nerve damage from surgery, nerve block, other factors, or a combination of these. We do not have any preliminary data indicating the duration of numbness as a separate entity from the duration of analgesia. In our preliminary data (published), the analgesic duration (with or without numbness) upper bound of the 95% confidence interval is 49 hr. By definition, the 95% interval (30-49 hr) is the interval representing that we are confident that the mean lies within this interval 95% of the time. So with the conservative 48 or 49 hr “upper bound” as the possible mean, and with a standard deviation of analgesic duration being 14 hr, we will apply a “mean and standard deviation” principle of “nerve damage” possibility. If the mean is 48 hr, and the standard deviation is 14 hr, then 97.5% of these nerve blocks’ numbness will dissipate by 76 hr (i.e., mean plus 2 standard deviations). For simplicity, if any patient has numbness (i.e., both analgesia and numbness, but not analgesia without numbness), beyond 72-76 hr after injection, then the participant will be referred (presumably while still in the hospital) to the Physical Medicine and Rehabilitation Service for initial evaluation, with subsequent referral to neurosurgery if deemed appropriate based on electromyography (EMG), imaging, or other workup. If minor symptoms of paresthesiae with pain and/or weakness persist over time, patients will be similarly referred to the Physical Medicine and Rehabilitation Service for outpatient workup, and these events will be recorded in study logs.

ISOC MMPNA Nerve Blocks From July 1, 2011 until December 31, 2014, there were a total of 1830 patient-block encounters involving our ISOC MMPNA program, entailing the routine use of 3-4 drugs in peripheral nerve blocks. At our institution, the incidence of EMG-documented nerve damage

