6.4 Inclusion/Exclusion Criteria

Inclusion Criteria:

Subjects must meet all of the following inclusion criteria to be eligible for participation in this study.

1. Age between 18 and 85, and undergoing a total knee or hip replacement.
2. Fluent in English, decision competent, willing and able to provide written informed consent, and able to complete the study's schedule of assessments.
3. Able to walk >3m without an assisting device.
4. Have a BMI $\leq 40 \text{ kg/m}^2$.

Exclusion Criteria:

Subjects who meet *any* of the following exclusion criteria will not be enrolled in this study.

1. Current participation in another orthopedic/PT/rehab/anesthesiology interventional clinical trial.
2. Are at significant behavioral risks or have refractory major psychiatric disorders.
3. Revision surgery on the same extremity.
4. Have an ASA Physical Status classification of 4 or higher.
5. Have been diagnosed with clinically significant neuropathy with its origins in either diabetes or other causes; have neuromuscular disease that would influence data collection.
6. Have a surgically-fused lumbar spine, or a spinal cord simulator, or other condition that would contraindicate or prohibit the conduct of spinal anesthesia.
7. At significant risk for postoperative substance abuse, or immediate-postoperative substance abuse withdrawal symptoms (alcohol, cocaine, enrolled in methadone or buprenorphine opioid withdrawal programs, etc.). Previous or current use of marijuana will not be an exclusion for study enrollment.
8. Are undergoing TKA/THA for a tumor.
9. Have contraindications (e.g., anaphylaxis) to any of the study drugs.
10. Have a systemic fungal infection.
11. Have a known hypersensitivity to bupivacaine hydrochloride or to any local anesthetic of the amide-type or to other components of bupivacaine hydrochloride solutions.
12. Have a known or suspected buprenorphine hypersensitivity (not including nausea and/or vomiting).
13. Have a GI obstruction.
14. Have paralytic ileus.
15. Pregnant women
16. Have had a kidney or liver transplant.

Veteran subjects will not be excluded from participation based on smoking status, diagnosis of obstructive sleep apnea, or baseline monitored consumption of therapeutic opioids for documented

medical indications; instead, these variables will be codified and quantified for subsequent covariate statistical analysis. Prior to study enrollment, the principal investigator has the final decision regarding patient eligibility.

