APPENDIX 1: Study Calendar

	Screening Visit ^a	Baseline Visit	Day of surgery		Post-Op Day 1	Post-Op Day 2	Post-Op Day 3	Post-Op Day 4	Post-Op Day 5	Follow-Up Visit 1 ^d	Follow-Up Visit 2 ^{c, e}
			Pre-Procedure	Post-Procedure							
Clinical Assessments											
Informed Consent	X										
Determine Eligibility	X										
Demographics	X										
Orthopedic & IMPACT evaluation		X									
Crude Sensation in L2-L4 & L4-S3		X			X	X	X	X	X		X
Straight Leg Raise & Range of Motion		X			X	X	X	X	X		X
Functional Independent Measure (FIM)		X			X	X	X	X	X		X
Standing Balance Test		X			X	X	X	X	X		X
Single Leg Balance Test ^g		X									X
Gait Speed		X			X	X	X	X	X		X
Repeated Chair Stand Test		X				X	X	X	X		X
Stair Climbing Time		X									X
Physical Therapy/ Therapeutic Exercises					X	X	X	X	X		
Comorbidity (CIRS)		X									
Interim Changes											X
Discharge Disposition											X
Opioid Consumption					X ^g						
Anesthesia/Study Drugs			X								
Adverse Events		X	X	X	X	X					
Concomitant Medications		X	X	X	X	X					

	Screening Visit	Baseline Visit	Day of surgery		Post-Op Day 1	Post-Op Day 2	Post-Op Day 3	Post-Op Day 4	Post-Op Day 5	Follow-Up Visit 1	Follow-Up Visit 2 ^{c, e}
			Pre-Procedure	Post-procedure							
Questionnaires											
SFMPQ-2 ^b		X	X	X	X	X	X	X	X		X
DVPRS		X	X	X						X	X
DVPRS- in hospital ^b					X	X	X	X	X		
ORSDS ^b		X			X	X	X	X	X		
QOR-15 ^b		X			X	X	X	X	X		X
WOMAC		X									X
SF-8 ^b			X		X	X	X	X	X	X	
SF-36		X									X
Falls Questionnaire		X			X	X	X	X	X		X

a. The screening visit and baseline visit can be completed on the same day.

b. On post-op hospital days and post-op week 6 follow-up visits, these questionnaires will be completed before the subject has their first physical therapy session for the day.

c. If a patient decides to withdraw from the study after having their surgery, or is withdrawn by the study team during or after their surgery, they will be asked to complete Follow-Up Visit 2.

d. Follow-up visit 1 will occur with the patient's already scheduled standard of care follow-up orthopedic visits. Follow-Up Visit 1 may be performed as a phone call if necessary.

e. Follow up visit 2 will be scheduled to coincide with the patient's standard of care follow-up orthopedic visits.

f. Patient must pass the standing balance test first, before the single leg balance test can be attempted.

g. Opioid consumption will stop being collected at the time of the patient's discharge.

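### The sensory examination defines normal only as equal feeling in both legs, so a partial deficit matched by the other leg is coded normal

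*Combined protocol and SAP*

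**What the plan says.** Section 4.3 has the tester "touching lightly the patient in the specified anatomic distribution of L2-L4 and L4-S3 bilaterally" while the patient's eyes are closed. The answer is then classified. "The patient is asked if the sensation is of equal intensity on both sides (normal), or if one side feels less than the other" gives the first two responses, and the sentence goes on "or is unable to be felt (diminished or absent". No other standard for normal is given: neither an unaffected area of skin nor the patient's own earlier result.

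The study calendar (Appendix 1) lists "Crude Sensation in L2-L4 & L4-S3" at Baseline, Post-Op Days 1 to 5 and Follow-Up Visit 2, which is seven columns. It is not marked in either day-of-surgery column or at Follow-Up Visit 1. No other sensory test is on the calendar.

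On eligibility, section 6.4 removes neuropathy only when it has been diagnosed and is clinically significant. Its criterion on previous joint surgery is limited to "Revision surgery on the same extremity". Diabetes is a randomization stratum (sections 4.1 and 4.2), so diabetics are expected in the sample.

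**The concern.** Whether the four-drug block prolongs numbness as well as pain relief is one of this study's own questions. Section 2.1 distinguishes analgesia from numbness and expects numbness to hold back physical therapy. Section 5.2 says the design will record both phases accurately and that no preliminary data exist on either. Section 7.3 concedes that it is not known whether the four-drug mixture gives longer unwanted numbness than the local anesthetic alone.

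A purely comparative test answers that question only when the comparison leg is normal. If it is not, a partly numb blocked leg can be recorded as normal, and the numb phase appears to have ended, or never to have occurred, in that patient. At stake is the description of numbness by arm, not the primary analysis.

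**Working it through.** No figure in the plan depends on this point, so there is nothing to recompute. The check applies the coding sentence of section 4.3 to each possible state of the two legs.

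| Operated leg | Other leg | Coding under section 4.3 | Correct for the operated leg? |
|---|---|---|---|
| Reduced | Normal | One side less: diminished | Yes |
| Absent | Normal | Unable to be felt: absent | Yes |
| Reduced | Equally reduced | Equal: normal | No |
| Normal | Reduced | One side less: diminished | Only if the side is recorded, which the text does not require |
| Absent | Absent | Equal, and also unable to be felt | Not determined |

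The third row is the fault. Whether it hides a block effect depends on the state before surgery:

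1. **Both legs equally and mildly reduced at baseline, and the block reduces one further.** The operated leg now feels less than the other and is coded diminished. The block effect is seen, although the baseline was coded normal.
2. **Only the other leg reduced at baseline, and the block brings the operated leg to the same level.** Baseline shows an asymmetry. The postoperative examination shows equality and is coded normal. The block effect is missed, and the record looks like recovery.
3. **Both legs normal at baseline and both equally reduced afterwards.** Coded normal. The deficit is missed, whatever its cause.

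Cases 2 and 3 are therefore the false negatives. Case 2 requires an abnormal other leg. Section 6.4 limits this but does not remove it, since undiagnosed or milder neuropathy and earlier surgery on the other leg are both allowed.

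Neighbouring tests in section 4.3 do not share the weakness. Range of motion is measured on each side in degrees, and the straight leg raise is scored on each side against a fixed angle of 20 degrees. Only the sensory test uses the other leg as its sole standard.

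On sensitivity to a single miscoding, section 4.1 plans 20 control and 80 four-drug patients per procedure. One miscoded patient moves the proportion recorded as numb by 1/20 = 5 percentage points in a control group and by 1/80 = 1.25 points in a four-drug group. This shows how much one patient weighs, not how many are affected.

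**The case against.** The strongest defence is that the block is one-sided, so the opposite leg is a natural comparator for a two-minute test that the protocol itself calls crude. In the common case of a normal other leg, and in case 1 above, it works. That stands, and it is why the side-to-side item should be kept. It does not answer cases 2 and 3.

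A second defence is that section 4.3 refers to a manual of operating procedures, and section 4.4 to data forms and a data dictionary, none of which are available here. The forms may already record each leg. That also stands: the criticism is of the rule as written in the protocol. For the same reason, it cannot be said that baseline will be ignored in analysis, only that the protocol specifies no analysis of this examination.

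A reader might infer more than the documents support:

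- **That all numbness in both legs is coded as none.** It is not. The sentence has a response for feeling that is lost. Only equal partial reduction is clearly coded normal, and loss on both sides is unspecified.
- **That the spinal makes bilateral numbness likely at these examinations.** It is true that "All patients will receive a standardized bupivacaine spinal anesthetic". But section 2.1 describes the spinal as wearing off "later in the day after surgery", most naturally read as the day of surgery, and the first postoperative sensory examination is on Post-Op Day 1. No spinal duration in hours is given, so residual spinal block at an examination would be an assumption.
- **That the fault disables the referral rule.** Section 5.2 acts "if any patient has numbness (i.e., both analgesia and numbness, but not analgesia without numbness), beyond 72-76 hr after injection" but names no measurement as its trigger. Section 4.3 says the clinical assessments are not done for safety, and section 9.2 has patients questioned routinely about adverse events.

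**Conclusion.** The point holds in a narrow form, and its severity is minor. As written, the rule codes as normal an equal partial reduction in both legs, or a partial deficit in the blocked leg matched by an already abnormal other leg. It leaves bilateral absence uncoded.

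The number of patients affected is probably small and cannot be estimated. The documents give no frequency of abnormal sensation in the other leg. Even an assumed frequency would be only an upper bound for case 2, because the block deficit must also match the existing one. Allocation is randomized and stratified by diabetes, so no bias between arms in a known direction is shown.

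The sensory examination is not in the outcome list of section 5.1 and does not enter the 24-hour SF-MPQ comparison. The consequence is confined to describing numbness and separating the two phases of analgesia, for which this is the only scheduled sensory record.

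The conclusion rests on two assumptions: that the data form follows the text of section 4.3, and that some enrolled patients have an other leg that is not normal.

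**What to change.** Revise the Crude Sensory Examination paragraph in section 4.3 and its form as follows:

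- Record each leg and each distribution (L2-L4 and L4-S3) separately as normal, reduced or absent. State on the form what the touch is judged against, for example skin outside the blocked distributions.
- Keep the side-to-side comparison as an additional item, with the weaker side noted. It catches a leg already reduced at baseline that becomes more so, which a three-level grade would miss.
- Code equal but reduced feeling as diminished, and loss in both legs as absent in each.
- Define block numbness as new reduction in the operated leg relative to the patient's own baseline examination, which is already on the calendar.

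The cost is one revised paragraph and form and a few seconds per examination, with no added visit or staff. The drawback is that patients already examined stay on the old coding. Appendix 2 mentions 22 enrolled by Amendment 6 and gives no later count. Their sensory data should be flagged and shown separately, or re-coded only where the source records allow. Nothing in this change alters treatment or the referral rule.

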4.4 Data Collection

Primary Outcome – Pain

Pain - Pain will be measured by the Short-Form McGill Pain Questionnaire (36). (SF-MPQ, version 2) and the Defense and Veterans Pain Rating Scale (DVPRS, which entails a 0-10 numeric rating scale along with step-function visual cues, color-coded visual cues, and verbal descriptors of pain intensity). The specific aim is the 24-hour pain severity as measured by the SF-MPQ. The DVPRS will be used to assess (i) “rebound pain” for pain with movement, compared with baseline, during and after nerve block analgesic effects are experienced and (ii) “block duration” (11) for time interval between block placement and peak postoperative DVPRS score with movement.

Exploratory Outcomes – Physical Function, Other Symptoms, and Recovery from Anesthesia

Data will be recorded by the research coordinator and/or VAPHS Staff Physical Therapists and/or “without compensation” (WOC) physical therapists hired through the University of Pittsburgh specifically for the care of study patients.

Data Management System

Data management will be coordinated at VAPHS by StatCore. Data entry will be primarily performed using the VA’s REDCap software (https://vhacdweb05.vha.med.va.gov/redcap_v6.0.27/index.php?pid=1440) via laptop or desktop personal computers. Data will never reside on the data collection devices, which serve only as portals to the password protected database. Only authorized members of the study team will have access. Data will reside on the VA Informatics & Computing Infrastructure (VINCI) server – which is also password protected and independent from all other servers. Data will be downloaded from the REDCap server by StatCore for analytic and data management purposes. Downloaded data will reside on a password-protected VAPHS secure shared drive. REDCap is a secure web-based platform that can only be accessed through the VA intranet, and it is situated behind the VA firewall. Account login information is required, and then the data are stored on the REDCap server. The data to be entered (and catalogued in a detailed data dictionary) are password-protected within REDCap via login requirements, and the downloaded data are secured by permission only access to the shared drive (\\\whapthshare\Nerve_Block_Study\).

Data collection forms have been designed as paper documents (in Microsoft Word) to allow the full research team to collaborate on content; these paper documents are also being submitted to regulatory (IRB, FDA) and sponsoring (DoD) entities. If modifications to the data collection forms are required, StatCore will maintain versioning control (for both paper versions and the REDCap versions) so that new form versions will be released with prior announcement, a clear and dated history of changes will be maintained, and the final dataset will contain compatible data for analysis.

Across all data collection forms, point-of-entry data checks will be developed to ensure complete and accurate data, ensuring appropriate data precision, guarding against missing or out-of-range data, and prompting for correction of illogical data (e.g. post-surgical procedures dated prior to surgery date). Branching logic will be used as is feasible to ensure that only relevant questions are presented (e.g. if the question “Ever smoked cigarettes?” is answered “No”, subsequent questions about smoking history are skipped). The system maintains a full audit trail, identifying each change to the entered data both by date/time and person, and recording both prior and current values, to ensure recovery of inadvertently changed data. It also provides user roles that define read, write, change, and delete privileges on an individual data collection form basis.

Documentation

Working with the study PIs and coordinators, the Clinical Trial Center and StatCore will finalize a Manual of Operating Procedures (MOP, currently in draft phase) to standardize all procedures and staff training in areas such as patient recruitment, measurement, and assessment, as well as data entry, management, and security.

A comprehensive data dictionary and code book has been created during study startup, and will be maintained throughout the study, logging any data field changes or coding changes. This dictionary will identify and characterize all fields available for analysis, and will provide a useful reference document for continuing analysis of the study data. We anticipate that the final versions of the MOP and data dictionary will be available for regulatory or related reviews approximately 12-15 months after study inception.

Confidentiality and Identifiers

All study subjects will be assigned unique study identifiers that will be used to identify all data stored within the data management system. The identifiers will contain no names, social security numbers, or medical record numbers. Patient contact information will be maintained by the study coordinator in locked files separate from the research data. No personal information concerning study participants will be released without participants’ written consent, and participants will not be identified by name in any publication of research results.

